1.3.2 Criteria for the selection of subjects

Location:

This study will take place at Atlanta Women's Center (AWC), a free-standing abortion clinic in metro-Atlanta that offers abortion services to women up to 23 weeks 6 days gestation.

This clinic operates 4 days per week (Wednesday through Sunday) with a clinical volume of 15 to 45 abortions per day. As abortion services are limited in the southeastern region of the United States, women often travel from other states, including Tennessee, Alabama, Florida,

Mississippi, North Carolina and South Carolina to receive care at this clinic. Approximately 4800 women are seen annually at AWC, with 720 women having abortions under local anesthesia and 3740 women receiving deep sedation anesthesia. Approximately 3320 women are 6-12 weeks GA, 800 women are 13-18 weeks and 340 women are over 18 weeks. Based on the patient volume, we do not anticipate any difficulty in recruiting patients to complete this study within the timeline presented. Misoprostol for cervical preparation is given prior to cases at 10 to 14 weeks per provider preference. Local anesthesia is offered as an option up to 16 weeks, however most cases performed with local anesthesia are less than 14 weeks, with the later gestational ages performed with deep sedation.

AWC, where [name] is the medical director and the study will be conducted, has documented success in participating in and recruiting for several industry sponsored and investigator initiated research studies: a randomized trial of levonorgestrel compared to

Table 1: Outcome measures and covariates	
Primary outcome	
Pain score validated on a 100mm VAS scale measured at time of start of uterine evacuation
Secondary outcomes:	
Pain on VAS scale: preoperatively, completion of procedure (removal of speculum), 10 and 30 min following procedure in the recovery room, at time of dischargeMedication use: pain and nausea medication used during and after procedureNausea/vomiting: pre op and post op nausea per VAS and episodes of vomitingAnxiety: preoperative state anxiety inventorySide effectsPostop assessment via phone on POD#1: pain, nausea, vomiting, and overall clinic experience
Covariates of interest:	
AgeGravidity, parity, prior abortionsBMIGestational agePreoperative medsCurrent or history of drug abuseCurrent or history of psychiatric disorderIndication for procedureExpectation of painPain experience with prior abortionSmoking

ulipristal for emergency contraception (LIFE) study through Washington University in St. Louis, and a prospective cohort study of medical abortion through 11 weeks conducted with Gynuity. This study will benefit from the existing research infrastructure and will resource share for recruitment and enrollment with another study at this site evaluating post-abortion contraception.

Participation selection:

Women who attend the AWC for an abortion will be approached during their preoperative evaluation to determine interest in participating in the study and if so, will be consented for the study and then screened for eligibility. We will enroll a total of 133 women. A baseline survey given after enrollment will collect covariates of interest that may impact a woman's abortion pain experience.

The enrollment of participants is as follows:

Group A: This is the placebo group. This group will receive local anesthesia per clinic protocol PLUS placebo 1-2 hours preoperatively.

Group B: This is the gabapentin group. This group will receive local anesthesia per clinic protocol PLUS Gabapentin 600mg 1-2 hours preoperatively.

Gabapentin 600mg was selected as a well-tolerated intermediate dosage with benefit proven in prior preoperative studies. Multiple post-operative doses in addition to the pre-operative dose had no significant effect on VAS scores at 24 hours, thus favoring single dosage [9].

Power Calculation:

A 100-mm pain visual analog scale has been shown to be useful for the evaluation of pain in prior pain abortion research [7, 18], with a 30% difference on a 100 mm-VAS scale, or 13-mm to 22-mm difference, as clinically meaningful [19, 20] [25]. Assuming a standard deviation of 26 mm on the 100-mm VAS scale [7], enrolling 96 women will provide us with

an 80% power, using a p-value of 0.05, to detect a 15-mm difference on a 100-mm VAS among women presenting for abortion. The enrollment of 96 women is estimated based on a sample size for a t-test. This sample size is adjusted based on the ARE (asymptotic relative efficiency) of the Mann-Whitney U test statistic. The ARE is based on distribution, which is unknown here. Since the ARE for the Mann-Whitney is never less than 0.864, the sample size from the t-test above will be divided by this value. This creates a sample size of 111 women. To account for a potential 20% loss to follow up, the target enrollment goal will be increased to 133 total women for participation in this study.

Inclusion and Exclusion Criteria:

Inclusion criteria include:

- Women ≥ 18 years-old
- Presenting for a surgical abortion
- Fluency in English and able to provide informed consent
- Has a driver to take them home

Exclusion criteria include:

- Allergy, sensitivity or contraindication to gabapentin
- Severe renal disease
- Currently using gabapentin or pregabalin
- Contraindication to outpatient abortion under local anesthesia

Although patients on any chronic pain medications or with pre-existing pain conditions or history of alcohol or drug use may have a different metabolism or effect of the drugs, these women will not be excluded. Rather, data will be collected on these factors to evaluate the impact of these factors on study outcomes.

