1.3.3 Subject recruitment and allocation

All recruitment, consenting, screening, and enrollment questions will be asked by trained study staff in a private room.

Recruitment:

We will be recruiting until a total of 133 women are randomized. The proposed research will take place at Atlanta Women's Center (AWC). Women who attend the AWC for an abortion will be approached during their preoperative evaluation. The flow of steps to assess women presenting for abortion occur in the following order: ultrasound for gestational age, blood draw to assess hemoglobin and Rh factor, options counseling to determine whether surgical abortion is chosen, financial payment, and nurse preoperative review. Trained research staff will approach these women to determine interest in participating in the study, consent those interested in participating, and then participants will be screened for eligibility. A standard recruitment script will be employed (Appendix A). We will enroll participants after financial counseling and before nurse preoperative review. Consent will be obtained at time of enrollment.

Screening and consent:

Individuals who are interested in participating will review the informed consent and eligibility screening. We will screen for eligibility using an eligibility checklist (Appendix A). Patient contact information will be collected at this time. Enrollment will occur after financial counseling, and consent will be obtained at time of enrollment. Following enrollment, the patient's medical history will be reviewed by a clinician to ensure study eligibility. Randomization will occur and intervention will be received after enrollment. The study drug (intervention or placebo) will be dispensed by the PI, Clinic Director, or Clinic Staff Nurse. Both the Clinic Director and Clinic Staff Nurse are registered nurses with required CITI training.

Potential subjects will typically do their 24hr consent over the phone prior to presenting to the clinic. Thus, the preoperative evaluation and procedure both occur on the same day. We are not approaching any potential subjects for interest in the study until after they have selected local anesthesia and paid for their procedure.

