1.3.6 Follow-up procedure

On the day following the procedure (approximately 24 hours after the abortion), study staff will contact the participant to complete the follow-up questions. The participant will be contacted via email, text communication and telephone. Upon completion of the questions, an additional \$20 will be added to the original gift card.

Withdrawals, losses, and deviations:

Randomization to the study method will occur after completion of all intake forms and consent, immediately before the pill is to be taken, thus reducing the possibility of withdrawal after randomization. Any significant medical history will be reviewed prior to enrollment with a clinician at the clinic to ensure study eligibility. Primary outcome measures and most secondary outcome measures will be assessed immediately before, during or after the abortion procedure, thus any loss to follow-up will be limited to those who consent to, but change their mind while waiting for their procedure. Based on current clinical practice at this clinic, withdrawal after consent is extremely rare. Our secondary outcomes assessed post-operatively after discharge will be collected via telephone. We will maximize completion of these assessments through the following steps: participants will be told beforehand about the telephone contact following the procedure, a cellular telephone number will be collected and tested at the clinic, a secondary phone number and email will be collected as a backup, participants will be given a contact number for the study coordinator should they have any challenges with receiving phone calls, and participants will receive an additional \$20 sent to their gift-card following the completion of their phone assessment. Subjects will be considered lost-to-follow-up if they have not responded to the follow up survey within 48 hours after their procedure. As we anticipate some loss to follow-up for our secondary outcome on post-operative day 1, we have adjusted our study enrollment to provide some accommodation for 20% loss to follow-up.

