1.3.10 Data analysis

We will compare groups on the primary continuous outcome measure (pain score on 100-mm point VAS) using T-tests and Mann-Whitney U test. Chi-square and T-tests will be used to evaluate secondary outcomes for categorical and continuous variables, respectively. Baseline characteristics will be evaluated for potential interaction or confounding with primary and secondary outcomes.

All available data from completed questions will be used for analysis, including partially completed surveys. Participants may request that their data not be used for analysis if a request is received prior to analysis as mentioned in the consent form. A statistician will be consulted to assist with the analysis as needed.

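### The 133 target is 111 plus 20%, which keeps 111 evaluable women only up to 16.5% loss, not the stated 20%; a minor arithmetic error to correct in wording

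*Combined protocol and SAP*

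**What the plan says.** The power calculation in section 1.3.2, repeated in 1.3.11, has three steps. A t-test with SD 26 mm needs 96 women for "an 80% power, using a p-value of 0.05, to detect a 15-mm difference on a 100-mm VAS". Dividing by 0.864, the lower bound of the asymptotic relative efficiency (ARE) of the Mann-Whitney test, raises the number: "This creates a sample size of 111 women". Then: "To account for a potential 20% loss to follow up, the target enrollment goal will be increased to 133 total women". Section 1.3.3 fixes the end of recruitment at the same figure: "We will be recruiting until a total of 133 women are randomized".

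Neither sample-size section says which outcome the 20% refers to. Section 1.3.6 does: "As we anticipate some loss to follow-up for our secondary outcome on post-operative day 1, we have adjusted our study enrollment". It defines loss by the follow-up survey ("Subjects will be considered lost-to-follow-up if they have not responded to the follow up survey within 48 hours after their procedure") and says of earlier dropout: "Based on current clinical practice at this clinic, withdrawal after consent is extremely rare". Section 1.3.10 adds: "All available data from completed questions will be used for analysis, including partially completed surveys".

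**The concern.** An allowance for loss should leave the required number once the loss has happened. Since loss is a share of those enrolled, the requirement has to be divided by one minus the loss rate. The plan appears to have added 20% of the requirement instead, which gives a smaller number and a lower tolerance than the one claimed.

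The same sentence has a second difficulty. It applies the 20% to a number derived for the primary outcome, while section 1.3.6 says the allowance was made for a secondary outcome collected the next day. A reader of the power section alone would expect a fifth of the primary data to be missing.

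At stake is the justification for 133, the enrolment target in sections 1.3.2, 1.3.3, 1.3.11 and 1.6, and possibly some power if primary outcomes really were lost at that rate.

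**Working it through.** **Inputs.** From 1.3.2 and 1.3.11: difference 15 mm, SD 26 mm, significance level 0.05, power 80%, ARE bound 0.864, loss 20%. Two assumptions are mine, because the plan states neither: a two-sided test (this reproduces 96; one-sided gives 76) and 1:1 allocation. Neither affects the step from 111 to 133.

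**1. Reproducing the plan's figures.**
- t-test size by normal approximation: n per arm = 2 × (1.96 + 0.8416)² × 26² / 15² = 47.16, so 48 per arm and 96 in total. This agrees with the plan.
- ARE step: 96 / 0.864 = 111.1, so 111. This agrees.
- Loss step: 111 × 1.2 = 133.2, so 133. This is how the plan's figure arises.

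**2. The loss step done on those enrolled.**
- N = 111 / (1 − 0.20) = 138.75, so 139 (140 for equal arms). Check: 139 × 0.8 = 111.2.
- Rounding does not explain the gap. Starting from 111.11, the two routes give 133.3 and 138.9.

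**3. What 133 tolerates.**
- 133 − 111 = 22 women, and 22 / 133 = 16.5%.
- At 20% loss: 133 × 0.8 = 106.4, about 106 women, 5 short of 111.
- Gap in enrolment: 139 − 133 = 6 women, and 6 / 133 = 4.5%.

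**4. Effect on power for 15 mm.** Worst-case power uses an effective size of 0.864 × N. Under the normal approximation, power = Φ(15 / (26 × √(4 / (0.864 N))) − 1.96). The noncentral t version is shown beside it.

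| Evaluable women | Worst-case ARE, noncentral t | Worst-case ARE, normal approximation | Plain t-test, noncentral t |
|---|---|---|---|
| 106 (20% loss) | 78.0% | 78.8% | 83.7% |
| 111 (requirement) | 79.8% | 80.6% | 85.4% |
| about 120 (10% loss) | 82.8% | 83.5% | – |
| 126 (5% loss) | 84.7% | 85.3% | – |
| 133 (no loss) | 86.6% | 87.1% | 91.0% |

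Falling from 111 to 106 costs 79.8 − 78.0 = 1.8 points, or 80.6 − 78.8 = 1.8 points.

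**5. Which outcome loses data.** Section 1.3.6 counts a woman as lost when she does not answer the follow-up survey within 48 hours. Her pain score at evacuation has been recorded by then, and section 1.3.10 keeps whatever data are available. She therefore still contributes to the primary analysis. The 5% and 10% rows illustrate modest loss; the plan puts no figure on loss before the primary outcome.

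**The case against.** The strongest reply is that nothing of substance follows. Section 1.3.6 places the loss on the day 1 survey, and sections 1.3.6 and 1.6 stress that the primary outcome is measured on the day of the procedure. The figure of 111 is itself pessimistic, because it uses the lowest possible ARE. Even 106 women exceed the 96 required for the t-test, which section 1.3.10 names alongside the Mann-Whitney test. With 106 women the Mann-Whitney test stays at or above 80% power unless its ARE is below about 0.89 (94.3 / 106, normal approximation) or 0.91 (96.3 / 106, noncentral t); at an ARE of 0.955 its power is about 82%. It can also be said that the plan never promises in so many words that 111 will remain, and that 1.3.6 speaks only of some accommodation.

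Most of this stands, and it limits the importance of the point: the primary analysis is not under threat. It does not make the sentence correct. The natural reading of an increase made to cover 20% loss is that the requirement survives that loss, and it does not. If the 20% concerns only day 1, then 1.3.2 and 1.3.11 misdescribe why 111 became 133, since the plan sets no sample-size target for day 1 outcomes. The sentence needs correction on either reading.

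**Conclusion.** The point holds as a minor arithmetic error, stated in two sections. The target of 133 covers a loss of 22 women (16.5%), not 20%; covering 20% would take 139. If a fifth of primary outcomes were missing, worst-case power would be 78–79% instead of 80–81%. With the small loss that the plan expects before the primary outcome, worst-case power is higher: about 83% at 10% loss, 85% at 5% and 87% with none. The arithmetic from 111 to 133 rests on no assumption of mine. The power figures rest on the plan's SD of 26 mm, a two-sided test and equal allocation. The correction makes the sample-size statement true and consistent with section 1.3.6; it does not rescue the trial's power, which does not need rescuing on this account.

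**What to change.** Keep 133 and replace the inflation sentence in sections 1.3.2 and 1.3.11 with wording such as:

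> The target of 133 women is 111 plus 20%. It keeps 111 evaluable for the primary outcome with up to about 16% (22 women) missing primary outcomes. At 20% missing, 106 women would give about 78–79% power at the worst-case ARE of 0.864, and about 84% for the t-test. The anticipated 20% loss concerns the post-operative day 1 outcomes (see 1.3.6); little loss is expected before the same-day primary outcome.

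This preserves the derivation of 133, states its real tolerance and removes the mismatch with 1.3.6. The cost is wording in two sections, with no change to enrolment, conduct or analysis. The one drawback is a slightly less favourable stated tolerance. If the investigators do want 20% cover for the primary outcome itself, the target would have to be 139 (140 for equal arms), 6 or 7 more women; nothing in the plan suggests that this is needed.

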1.3 Design and Methodology

1.3.1 Research design and General Methodology Approach

This is a randomized double-blind placebo-controlled trial evaluating the impact of gabapentin given preoperatively on perioperative pain scores for women receiving a surgical abortion. Randomization will be done using computer generated random Fellowship in Family Planning Research Proposal Outline

numbers. Allocation concealment will be maintained by identically labeled sealed sequentially numbered pill containers. Gabapentin and placebo will be packaged in identical gelatin capsules and sealed by an independent pharmacy. Gabapentin and placebo gelatin capsules will be indistinguishable by appearance, thus maintaining double blinding.

Primary study outcomes: Our primary outcome measure will be pain score using a 100-mm visual analog scale (VAS) measured intraoperatively at time of evacuation.

Secondary outcomes: We will also be measuring pain on the 100-mm VAS preoperatively immediately prior to the procedure, at completion of the procedure (removal of the speculum), 10 minutes and 30 minutes following the procedure, and at discharge. Nausea and vomiting will be assessed during the same time intervals using a 100-mm VAS scale. Anxiety prior to the procedure will be measured using the preoperative state trait anxiety inventory. Side effects will be assessed using a checklist prior to discharge. We will also be contacting participants on post-operative day 1 to assess pain, nausea, vomiting, side effects and general satisfaction with the procedure (on a 5-point scale). The quantity and type of medications used perioperatively and post-operatively, including medications used at home in the 24 hours post-operatively, will be abstracted from the clinical record and assessed on the phone. Outcome measures will be collected on a tablet using a web-based password-protected relational database (REDCap). All VAS scale scoring and questionnaires will be completed using this database on a research-designated tablet.

Baseline Characteristics and Covariates:

We will collect baseline demographics, medical history (gravidity, parity, prior abortions (medical and surgical), gestational age, drug and alcohol use, psychiatric or sexual assault history, medications used at home and given at the clinic preoperatively, and indication for procedure (personal/social, fetal, or maternal health). This information will also be obtained using a research-designated tablet.

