1.3.4 Description of the drugs and devices to be studied

Gabapentin was originally approved by the U.S. Food and Drug Administration (FDA) in December 1993, for use as an adjuvant (effective when added to other antiseizure drugs) medication to control partial seizures in adults; that indication was extended to children in 2000 [21], and later approved for treating postherpetic neuralgia. In December 2004, the FDA granted final approval to a generic equivalent to Neurontin made by the Israeli firm Teva. It was originally synthesized to mimic the chemical structure of the neurotransmitter GABA. The mode of action of gabapentin is believed to be through its binding to the alpha 2 delta subunit of the DRN voltage-dependent calcium channels. This causes decreased entry of calcium into the nerve endings, resulting in decreased release of nociceptive neurotransmitter (glutamate, substance p, noradrenaline). Other proposed mechanisms of action include the binding to NMDA receptors, sodium channel receptors, monoaminergic receptors, and opioid receptors.

Overall, gabapentin is a safe drug. The most common side effects of its use include: dizziness, somnolence, fatigue, ataxia, peripheral edema, nystagmus, nausea and vomiting, asthenia, headache, weight gain, and amblyopia. Most of the side effects are associated with chronic usage. Other extremely rare side effects include: DRESS (drug reaction with eosinophilia and systemic symptoms), multi-organ hypersensitivity, withdrawal seizures (if given for epilepsy), suicidal behavior and ideation, neuropsychiatric reactions in pediatric patients (3-12 years of age), and sudden death.

Drug Interactions are rare and mild. Maalox or other aluminum or magnesium hydroxides decreases bioavailability of gabapentin by 20% if given at same time. Additionally, when used with hydrocodone or morphine, gabapentin may decrease the AUC. Abuse and withdrawal potential is low. The drug is almost entirely metabolized through renal metabolism, where it is eliminated unchanged in the urine, thus dosage adjustments are needed for patients with renal impairment. The half-life for the medication is 5-7 hours with a 2 hour time to peak plasma concentration.

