1.3.5 Admission procedure

After financial clearance, all participants who have opted for a surgical abortion with local anesthesia will be approached for interest in the study. A study interest card will be placed on their medical chart, and the participant will be accompanied by the financial counselor and taken to the designated research room. This designated research room is a private room located in AWC. The study team will then review the recruitment script with the patient. If the patient is interested in the study, then a member of the study team will consent the participant. Following consent and enrollment into the study, the participant will be taken to the clinical nurse. The nurse will review the participant's chart to ensure eligibility for surgical abortion and gabapentin administration. The participant will then receive the study drug or placebo. Following administration of the drug, the participant will return to the designated research room. The study staff will review the baseline questionnaire that includes demographic questions. Following completion of the questionnaire, the participant will continue to wait in the designated research room or preoperative area. One hour after the administration of the drug or placebo, the participant's chart will be placed back into rotation for surgical procedures. The study team will accompany the participant to the clinical lounge where they will gown and prepare for the procedure. The participant will then undergo the procedure in order of chart placement. Prior to initiating the abortion procedure, study staff will administer the preoperative questions. Staff will administer the intraoperative questions at the time of evacuation during the uterine aspiration, and at time of removal of the speculum at the end of the procedure. Immediately following the procedure, the study staff will follow the participant to the recovery room to complete the remaining questions assessed at 10 minutes, 30 minutes and at discharge. Per clinic protocol, patients remain in the recovery room for approximately 30-60 minutes after surgical abortion with local anesthesia. When the discharge questions are complete, the participant will receive a \$30 gift card and be reminded to expect a follow-up call the following day (post operative day #1).

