1.3.8 Laboratory and other investigations

Examinations will be performed prior to the surgical abortion that are in accordance with the standard of care. No additional laboratory studies will be performed for the clinical trial.

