Gabapentin is indicated for the management of postherpetic neuralgia in adults, as adjunctive therapy in the treatment of seizure disorder, and for chronic pain management. Gabapentin is contraindicated in patients who have demonstrated hypersensitivity to the drug or its ingredients. When gabapentin is taken for chronic use, side effects are noted. Drug reaction with eosinophilia and systemic symptoms, also known as multiorgan hypersensitivity, has occurred with gabapentin. These reactions can be fatal or life threatening. Typical symptoms include but are not limited to fever, rash, lymphadenopathy, hepatitis, nephritis, hematological abnormalities, myocarditis, or myositis. In the presence of signs or symptoms, prompt evaluation and discontinuation of gabapentin is warranted. Although rare, gabapentin can cause anaphylaxis and angioedema after the first dose or any time during treatment. The patient should be instructed to discontinue the medication and seek immediate medical attention.

During the controlled epilepsy trials in patients older than 12 years of age, the patients who received gabapentin (up to 1800mg daily) reported greater rates of somnolence (19%), dizziness (7%) and ataxia (6%) when compared to the placebo group. During the controlled trials in patients with postherpetic neuralgia taking doses of gabapentin up to 3600mg, patients reported increased somnolence (21% of the gabapentin arm vs. 5% of the placebo arm), and dizziness (28% of the gabapentin arm vs. 8% of the placebo arm). Patients should be carefully observed for signs of central nervous system depression, especially when gabapentin is used with other drugs with sedative properties.

Antiepileptic drugs (AEDs), including gabapentin, increase the risk of suicidal thoughts or behavior in patients taking these drugs for any indication. Patients should be monitored for the emergence or worsening depression, suicidal thoughts or behavior, and/or unusual changes in mood or behavior. Pooled analysis showed that patient randomized to one of the AEDs had approximately twice the risk of suicidal thinking or behavior compared to patients randomized to placebo. It should be noted that these trials had a median treatment duration of 12 weeks.

During the premarketing development of gabapentin, there were 8 sudden or unexplained deaths that were recorded among a cohort of 2203 epilepsy patients treated

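### The drug description says renal impairment calls for dose adjustment, but the criteria exclude only undefined severe renal disease and the blinded dose is fixed

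*Combined protocol and SAP*

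**What the plan says.** **Eligibility.** Section 1.3.2 has one renal exclusion, "Severe renal disease", with no cut-off or definition. A separate line excludes "Allergy, sensitivity or contraindication to gabapentin". The inclusion criteria require each woman to have a driver.

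**Dose and packaging.** For Group B, section 1.3.2 states: "This group will receive local anesthesia per clinic protocol PLUS Gabapentin 600mg 1-2 hours preoperatively". Section 1.3.1 states: "Gabapentin and placebo will be packaged in identical gelatin capsules and sealed by an independent pharmacy". Section 1.3.3 adds that the containers are opaque, numbered in sequence and filled by someone outside the study's conduct. No section describes adjusting the dose for an individual.

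**Drug description.** Section 1.3.4 describes gabapentin as cleared almost wholly by the kidney, "thus dosage adjustments are needed for patients with renal impairment". It names no grade of impairment and does not restrict the remark to repeated dosing.

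**Checks before dosing.** Section 1.3.3 has a clinician review the medical history for eligibility, and section 1.3.6 describes a similar review of significant history. In section 1.3.5 the nurse reviews the participant's "chart to ensure eligibility for surgical abortion and gabapentin administration". Section 1.3.6 places randomization just before the capsule is taken.

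**Laboratory.** The blood tests listed in section 1.3.3 are hemoglobin and Rh. Section 1.3.8 states: "No additional laboratory studies will be performed for the clinical trial".

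**The concern.** The drug description and the eligibility criteria draw the renal line in different places. The first speaks of renal impairment generally, the second of severe disease only. Women between the two lines are admitted by the criteria and, if allocated to Group B, are due an unadjusted dose, although the protocol's own account of the drug says such patients need an adjustment.

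The stake is participant safety on a small scale. Two careful staff members could reach different answers about the same woman, one relying on the exclusion list and the other on the drug description. If the question arose only after a container had been assigned, the outcome would be either an unadjusted dose or a randomized woman who does not take study drug.

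**Working it through.** The point is textual and the plan offers no figure to reproduce. The check is whether any other provision closes the gap.

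| Provision | Where | Does it cover non-severe renal impairment? |
|---|---|---|
| Renal exclusion | 1.3.2 | No. It stops at severe disease, undefined. |
| Exclusion for a contraindication to gabapentin | 1.3.2 | Not on the documents' own account. The drug information in section 2 says: "Gabapentin is contraindicated in patients who have demonstrated hypersensitivity to the drug or its ingredients". Renal impairment is not named there. |
| Fixed blinded dose | 1.3.1, 1.3.2, 1.3.3 | No. There is no adjustment step. |
| Clinician review of history | 1.3.3, 1.3.6 | Possibly, by clinical judgement. No renal rule is stated. |
| Nurse chart review | 1.3.5 | Possibly. It is specific to the drug, but no renal rule is stated. |
| Laboratory tests | 1.3.3, 1.3.8 | No renal test is listed, so the answer must come from history or the chart. |
| Remark that only one dose is given | End of section 2 | No. It discounts side effects of chronic use and does not mention renal dosing. |
| Recorded history and covariates | 1.3.1, Table 1 | Renal status is not listed. By contrast, section 1.3.2 explicitly keeps women on chronic pain medication or with alcohol or drug use, and says data on these factors will be collected. |

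No provision reconciles the two statements. Two provisions could catch such a woman in practice, but only by judgement that the protocol does not guide.

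**How many women.** The documents give no frequency of non-severe renal impairment in this population. Purely as an assumption, take 0.5% to 2% of the 133 to be enrolled:

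- low: 133 × 0.005 = 0.67 women, and 0.67 / 2 = 0.33 on active drug;
- high: 133 × 0.02 = 2.66 women, and 2.66 / 2 = 1.33 on active drug.

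That is roughly 0 to 1 woman in the active arm.

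**What reduced clearance would do.** This too is an illustration. With exposure (AUC) equal to absorbed dose / clearance, and half-life equal to 0.693 × volume / clearance, halving clearance at constant volume doubles both. The half-life of 5 to 7 hours in section 1.3.4 would become 2 × 5 = 10 to 2 × 7 = 14 hours. The halving is chosen for illustration and is not taken from the documents.

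**The case against.** **Section 1.3.4 is background.** It covers the drug's history, mechanism, interactions and elimination, and gives staff no instruction. A reader might infer that the protocol issues two opposing orders for the same woman. The documents do not support that: the only operative renal rule is the exclusion in section 1.3.2. What remains is a description and a rule that do not match.

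**The review steps may catch her.** A reader might also infer that a woman with known renal impairment would certainly pass review and be dosed. The documents do not say so. History and chart review come before a randomization done just before the capsule is taken, and the nurse's check extends to suitability for gabapentin. This stands, and it makes discovery after randomization unlikely. It does not remove the point, because these reviews check eligibility and the written criteria admit her.

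**The checklist is not visible.** Section 1.3.3 places the eligibility checklist in Appendix A, which is not in the available text. It may already define severe disease or ask about kidney problems. That stands as a limit on what can be said. A checklist item alone would still leave sections 1.3.2 and 1.3.4 in disagreement.

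**The exposure arithmetic shows no harm.** If exposure is proportional to dose, doubling it after 600 mg gives what 2 × 600 = 1200 mg would give at normal clearance, and section 1.2 cites single preoperative doses of 300 to 1200 mg. The arithmetic therefore does not show exposure outside the range the protocol relies on. This stands; it says nothing about which dose is right.

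**Discharge with drug still present is not specific to renal impairment.** With a 2-hour peak and a 5 to 7 hour half-life, this applies to the whole active arm, and every participant must have a driver. This also stands, as partial mitigation.

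**Conclusion.** The point holds as a minor inconsistency. The drug description calls for adjustment in renal impairment without limit of severity; the criteria exclude only an undefined severe category; the dose is fixed and blinded; and nothing in the available text connects the three. Followed as written, the plan admits women whom its own drug description says need an adjustment.

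The size is small. The figure of about 0 to 1 active-arm woman rests wholly on the assumed 0.5% to 2%. Sample size, power, the primary analysis and blinding are not affected. The documents do not support reading this as a demonstrated overdose risk or a failure of screening. The conclusion also depends on the unseen Appendix A containing nothing that settles the matter.

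**What to change.** The clinical leads should reconcile the Group B dosing text and the exclusion list in section 1.3.2 with the renal statement in section 1.3.4. Either the exclusion and the adjustment statement should cover the same category of renal function, or the protocol should state why a one-time dose does not need it. Which clinical rule applies is theirs to decide.

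The resulting line should be worded so that it can be answered from history, since no renal test is listed. It should be applied at the clinician and nurse reviews that already precede randomization, and the Appendix A checklist should be checked to match.

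The cost is one line of text and, depending on the rule chosen, possibly a few candidates becoming ineligible. No laboratory test, extra staff or change in sample size is needed.
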